9.4 ATTRIBUTION.....	27
9.5 REPORTING PROCEDURES FOR ALL ADVERSE EVENTS.....	28
9.5.1 Serious Adverse Event Reporting Procedures	28
9.5.2 Incyte Reporting	28
9.5.3 FDA Reporting	29
10. PHARMACEUTICAL INFORMATION	31

10.1	INVESTIGATIONAL AGENT	31
10.1.1	Ruxolitinib	31
11.	CORRELATIVE / SPECIAL STUDIES	33
11.1	BACKGROUND	33
11.2	RATIONALE FOR ANALYSIS	33
11.3	COLLECTION OF SPECIMENS.....	33
12.	STUDY PARAMETERS AND CALENDAR.....	33
12.1	STUDY PARAMETERS.....	34
12.1.1	Screening Evaluation	34
12.2	CALENDAR.....	35
13.	MEASUREMENT OF EFFECT	36
13.1	RESPONSE EVALUATION	36
13.1.1	Definitions	36
13.1.2	Disease Parameters	36
13.1.3	Response Criteria	36
13.1.4	Duration of Response	37
14.	RECORDS TO BE KEPT / REGULATORY CONSIDERATIONS.....	37
14.1	DATA REPORTING.....	37
14.2	REGULATORY CONSIDERATIONS.....	37
14.2.1	Written Informed consent	37
14.2.2	Subject Data Protection	38
14.2.3	Accessing Electronic Medical Records for University of Michigan Hospital and Health Systems	38
14.2.4	Retention of records	38
14.2.5	Audits and inspections	38
14.2.6	Data Safety and Monitoring Plan	39
15.	STATISTICAL CONSIDERATIONS.....	40
15.1	SAMPLE SIZE	40
15.2	ANALYSES	40
16.	REFERENCES	42
17.	APPENDIX A.....	45

SCHEMA

Pilot study to determine the efficacy of Ruxolitinib in secondary hemophagocytic syndrome.

STUDY SYNOPSIS

Disease : Secondary Hemophagocytic Syndrome (HPS)

Primary objective: To assess the efficacy of ruxolitinib 15 mg PO twice daily in patients with HPS.

Primary endpoint: Overall survival at 2 months.

Secondary objectives:

- 1) To assess the safety and tolerability of ruxolitinib in patients with HPS.
- 2) To determine the response rate, duration of response, progression-free survival, and overall survival in ruxolitinib treated subjects.

Exploratory objectives:

To assess inflammatory cytokines and markers of T-cell/macrophage activation (i.e. cytokines, sIL-2R, sCD163) as predictive biomarkers.

Inclusion Criteria:

- 1) Patients, or their legally authorized representative, must voluntarily provide written IRB-approved informed consent.
- 2) Males and females, 18 years of age or older at the time of enrollment.
- 3) Patients must meet the diagnostic criteria for HPS (at least 5 of the following):
 - fever
 - splenomegaly
 - cytopenia involving ≥ 2 cell lines (Hemoglobin < 9 g/dL; platelets $< 100,000/\mu\text{L}$; absolute neutrophil count $< 1000/\mu\text{L}$)
 - hypertriglyceridemia or hypofibrinogenemia
 - tissue demonstration of hemophagocytosis
 - low or absent NK cell activity
 - serum ferritin ≥ 3000 ug/L
 - soluble IL-2 receptor (CD25) > 2400 U/mL.
- 4) In the investigator's opinion, the patient has the ability to participate fully in the study and comply with all its requirements.

Exclusion criteria:

- 1) CNS involvement
- 2) Malabsorption
- 3) Pregnant or lactating female: all females of child-bearing potential must have a negative serum pregnancy test within 7 days of treatment
- 4) Has received any prior systemic therapy, excluding corticosteroids, within 7 days of treatment.

- 5) Estimated creatinine clearance <15mL/min
- 6) No active malignancy at the time of enrollment, except nonmelanoma skin cancers or carcinoma in situ. Patients with a prior history of malignancy are eligible if their malignancy has been definitely treated or is in remission and does not require ongoing adjuvant or cancer-directed therapies.
- 7) Active hepatitis B or hepatitis C or known HIV infection.
- 8) Known (and biopsy-confirmed) liver cirrhosis; or, a reported history of liver cirrhosis with a model for end-stage liver disease (MELD) score >20.

1. INTRODUCTION

1.1 Hemophagocytic Syndrome

Hemophagocytic Syndrome (HPS) is a disorder characterized by pathological activation of the immune system resulting in a systemic disorder characterized by excessive cytokine production and macrophage activation, culminating in cytopenias and evidence of hemophagocytosis on tissue specimens. The disorder can be sporadic or familial due to one of several mutations and is primarily seen in the pediatric population, with a reported incidence of 1 case per 3000 admissions¹. The actual incidence in adults is unknown and can be rarely sporadic, or secondary to viral infections, malignancy, or autoimmune disease.

HPS is a universally fatal disease if untreated. In adults, the median survival has been reported to be less than 2 months if diagnosis and treatment is delayed². Adult patients are treated with pediatric protocols with early institution of etoposide and steroids and consolidation with allogeneic stem cell transplant in appropriately selected patients if a familial form is identified³. Other treatment strategies have been attempted, including rituximab⁴, infliximab⁵, entarcept⁶, tocilizumab⁷, and alemtuzumab⁸. These anecdotal reports highlight the therapeutic potential of cytokine-targeted therapies in this disorder.

1.2 Ruxolitinib

1.2.1 Preclinical Data

Ruxolitinib (INCB018424 phosphate, INC424, ruxolitinib phosphate) represents a novel, potent, and selective inhibitor of JAK1 (Janus kinase 1) (inhibition concentration 50% [IC₅₀]=3.3 ± 1.2 nM) and JAK2 (IC₅₀=2.8 ± 1.2 nM) with modest to marked selectivity against TYK2 (tyrosine kinase 2) (IC₅₀=19 ± 3.2 nM) and JAK3 (IC₅₀=428 ± 243 nM), respectively. Ruxolitinib interferes with the signaling of a number of cytokines and growth factors that are important for hematopoiesis and immune function⁹⁻¹¹.

JAK signaling involves recruitment of signal transducers and activators of transcription (STATs) to cytokine receptors, activation, and subsequent localization of STATs to the nucleus leading to modulation of gene expression. Dysregulation of the JAK-STAT pathway has been associated with several types of cancer and increased proliferation and survival of malignant cells¹²⁻²³. In particular, this pathway may be dysregulated in the majority of

patients with Philadelphia chromosome negative myeloproliferative neoplasms (MPNs, including myelofibrosis [MF] and polycythemia vera [PV]), suggesting that JAK inhibition may be efficacious in these diseases.

During the Phase I and Phase II development program, ruxolitinib was assessed in healthy volunteers, subjects with various degrees of renal or hepatic impairment, in patients with rheumatoid arthritis, prostate cancer, multiple myeloma (MM), MF, PV and essential thrombocythemia (ET). Ruxolitinib is currently approved for the treatment of MF/ PV/ET, and is currently under development for the treatment of other hematologic malignancies, and solid tumors. Two pivotal Phase III trials in MF patients have been completed and one in PV patients is ongoing.

1.2.2 Clinical Data

Ruxolitinib is a potent, selective ATP-competitive inhibitor of JAK1 and JAK2 kinases, with an IC₅₀ of 3.3nM and 2.8nM, respectively. Ruxolitinib inhibits JAK signaling by targeting the cytokines that support transformed cells and are responsible for constitutional symptoms. It arrests growth factor signaling by inhibiting downstream STAT phosphorylation. Ruxolitinib has been administered to over 180 healthy volunteers as single, repeat single, or multiple doses of up to 10 days duration. Ruxolitinib has been administered to approximately 450 subjects with MF for periods of up to > 24 months, and over 100 subjects with prostate cancer, multiple myeloma, polycythemia vera or essential thrombocythemia for periods of up to > 24 months. In healthy volunteer studies, a transient, reversible decrease in neutrophil count has frequently been seen following dosing, which reverses after 12 to 24 hours off drug, suggestive that the neutropenia may reflect an effect of ruxolitinib blocking IL-6 signaling and causing neutrophil margination on blood vessel walls. In a repeat dose healthy volunteer study, neutropenia of any severity grade was seen in 22% of placebo subjects, 11% of subjects receiving 50 mg qd, 67% of subjects receiving 100 mg qd, 13% of subjects receiving 15 mg bid, 33% of subjects receiving 25 mg bid and 67% of subjects receiving 50 mg bid. Importantly, these neutropenia events were of Grade 1 or Grade 2 severity with a single instance of severe Grade 4 neutropenia that led to discontinuation of study drug in 1 subject receiving ruxolitinib at 50 mg bid (highest dose). The maximum tolerated dose in healthy volunteers was determined to be 25 mg bid and no dose limiting toxicities (DLT) were seen at 100 mg qd. A definitive QT study was carried out in 50 healthy volunteers, evaluating the effects of single doses of 25 mg or 200 mg ruxolitinib compared with placebo and 400 mg moxifloxacin (positive control). The overall conclusion was that there appeared to be no adverse impact on ventricular repolarization (no increase in QTcF) and little change in heart rate, QRS duration, and a slight, non-clinically significant, increase in PR interval with the administration of ruxolitinib. This agent is currently FDA approved for the treatment of patients with intermediate to high-risk myelofibrosis, including primary myelofibrosis, post-Polycythemia Vera myelofibrosis and Post-Essential Thrombocytopenia myelofibrosis based on pre-clinical activity in cellular assays driven by *JAK2V617F* and on the results of the phase III studies COMFORT-1 and COMFORT-2^{24,25}. In those trials, the agent was continuously dosed at 15-20mg PO twice daily (BID); currently, depending on platelet count, ruxolitinib is FDA approved from 5 mg BID to a maximum dose of 25mg BID. To further demonstrate the tolerability of this agent in other disease settings; pilot studies have

demonstrated, ruxolitinib was well tolerated in patients with psoriasis and rheumatoid arthritis studies²⁶. Ruxolitinib use has been associated with myelosuppression, thrombocytopenia, and anemia in patients with myelofibrosis. Other documented side effects include dizziness, headaches, bruising and traminitis.

1.2.3 Clinical Pharmacokinetics

Twelve Phase I, five Phase II, and two Phase III clinical studies were conducted to explore the clinical pharmacology of ruxolitinib in healthy volunteers and in patients with MF, ET, PV, subjects with renal or hepatic impairment, prostate cancer, MM or rheumatoid arthritis (RA).

- Oral absorption of ruxolitinib is rapid and nearly complete, with $\geq 95\%$ absorption indicating high in vivo permeability in the human gastrointestinal tract, consistent with a Biopharmaceutical Classification System (BCS) Class I compound. Mean peak plasma concentrations (C_{max}) is achieved 1-2 h post-dose.
- The effect of food on ruxolitinib exposure is minimal and is not expected to be clinically significant; as a result, the drug may be administered either with or without food.
- Dose proportional exposure is observed between 5 and 200 mg dose range with linear pharmacokinetics (PK).
- Plasma protein binding is approximately 97% in vitro. There is moderate distribution to organs and tissues with no long-term retention of drug-related material in preclinical species and limited drug penetration into the central nervous system (CNS) or across the blood-brain barrier.
- There is $>95\%$ [¹⁴C] drug recovery in a mass balance study with 74% and 22% of the dose excreted in urine and feces of healthy subjects, respectively. Less than 1% of the administered dose is recovered in urine and feces as unchanged parent drug.
- The mean terminal elimination half-life is ~ 3 h with no appreciable accumulation of either parent or metabolites with twice daily dosing.
- Metabolism is predominantly via the cytochrome P450 isozyme CYP3A4 to yield oxygenated and subsequent conjugated metabolites.
- Oxidative metabolites of ruxolitinib retain pharmacological activity albeit with one half to one fifth of the activity of the parent compound. Ex vivo pharmacokinetic/pharmacodynamic (PK/PD) analysis indicates that the sum total of 8 active metabolites contribute to 18% of the overall PD activity of ruxolitinib.
- When administering ruxolitinib with strong CYP3A4 inhibitors, the total daily dose should be reduced by approximately 50%.
- No dose adjustment is necessary when co-administering ruxolitinib with strong CYP3A4 inducers.
- In patients with severe [creatinine clearance (Cl_{cr}) < 30 mL/min] and moderate renal impairment ($Cl_{cr} = 30 - 49$ mL/min), the recommended starting dose based on platelet count should be reduced by approximately 50% to be administered twice a day. Patients on hemodialysis should initiate ruxolitinib with a single dose of 15 mg or 20 mg based on platelet counts with subsequent single doses only on hemodialysis days and following each hemodialysis session. Ruxolitinib doses should be titrated based on individual safety and efficacy.
- In patients with mild, moderate or severe hepatic impairment, the recommended starting dose based on platelet count should be reduced by approximately 50% with subsequent dose titration based on individual safety and efficacy.

- Baseline elevations in inflammatory markers such as tumor necrosis factor alpha (TNF α), interleukin (IL)-6, and C-reactive protein (CRP) noted in subjects with MF were associated with constitutional symptoms such as fatigue, pruritus, and night sweats. Decreases were observed in these markers over the 24 weeks of treatment with ruxolitinib, with no evidence that subjects became refractory to the effects of ruxolitinib treatment.

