4.2 Exclusion Criteria

The presence of any of the following will exclude a patient from study enrollment.

1. CNS involvement
2. Malabsorption
3. Known secondary HPS that is otherwise treatable (e.g. non-Hodgkin's lymphoma).
4. Pregnant or lactating female: all females of child-bearing potential must have a negative serum pregnancy test within 7 days of treatment; lactating females must discontinue breast feeding.

5. Has received any prior systemic therapy, excluding corticosteroids, within 7 days (or 5 half-lives) of treatment.
6. Estimated creatinine clearance <15 mL/min
7. No active malignancy at the time of enrollment, except nonmelanoma skin cancers or carcinoma in situ. Patients with a prior history of malignancy are eligible if their malignancy has been definitely treated or is in remission and does not require ongoing adjuvant or cancer-directed therapies.
8. Active hepatitis B or hepatitis C or known HIV infection.
9. Known (and biopsy-confirmed) liver cirrhosis; or, a reported history of liver cirrhosis with a model for end-stage liver disease (MELD) score >20.

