6.1.1 Ruxolitinib Administration

Patients will receive Ruxolitinib at 15 mg twice daily orally either on an empty stomach or with food for 4 weeks (28 days) in a 4 week (28 day) cycle. Ruxolitinib will be administered in continuous 28-day cycles. For patients unable to ingest tablets, ruxolitinib suspended in water may be administered through a nasogastric (NG) or percutaneous endoscopy gastrostomy (PEG) tube. Tablets should be suspended (1 tablet in ~40 mL water) in water and stirred for 10 minutes and administered within 6 hours of dispersion with an appropriate syringe. The NG or PEG tube should be rinsed with ~75 mL water following administration.

Ruxolitinib administration must be at least 1 hour before or after any other medications.

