6.2 General Concomitant Medications and Supportive Care Guidelines

Because there is a potential for interaction of Ruxolitinib with other concomitantly administered drugs through the cytochrome P450 system, the case report form must capture the concurrent use of all other drugs, over-the-counter medications, or alternative therapies. The Principal Investigator should be alerted if the patient is taking any agent known to affect CYP3A4. In patients who concurrently take strong CYP3A4 inhibitors and a platelet count of at least 50,000 the dose of ruxolitinib should be capped at 10 mg twice daily due to the concern for increased serum concentrations of ruxolitinib's active metabolites. Strong CYP3A4 inhibitors, including grapefruit juice, should be avoided whenever possible.

Patients should receive full supportive care, including transfusions of blood and blood products, cytokines, antibiotics, anti-emetics, etc when appropriate.

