7. DOSING DELAYS / DOSE MODIFICATIONS

Ruxolitinib will be dosed twice daily throughout the study. In the event a dose is missed, the subject should be instructed to take the next scheduled dose.

Dose Level	Ruxolitinib (BID schedule)	
	CrCl \geq 60	CrCl 15-59
Level 1 (starting dose)	15 mg	10 mg
Level -1 (reduction)	10 mg	5 mg
Level -2 (reduction)	5 mg	Hold

Event Name	Nausea
Grade of Event	Management/Next Dose for Ruxolitinib
\leq Grade 1	No change in dose
Grade 2	Hold until \leq Grade 1. Resume at same dose level.
Grade 3	Hold* until $<$ Grade 2. Resume at one dose level lower, if indicated.**
Grade 4	Off protocol therapy
*Patients requiring a delay of $>$ 4 weeks should go off protocol therapy.	
**Patients requiring $>$ two dose reductions should go off protocol therapy.	
Recommended management: antiemetics.	

Event Name	Vomiting
Grade of Event	Management/Next Dose for Ruxolitinib
\leq Grade 1	No change in dose
Grade 2	Hold until \leq Grade 1. Resume at same dose level.
Grade 3	Hold* until $<$ Grade 2. Resume at one dose level lower, if indicated.**
Grade 4	Off protocol therapy
*Patients requiring a delay of $>$ 4 weeks should go off protocol therapy.	
**Patients requiring $>$ two dose reductions should go off protocol therapy.	
Recommended management: antiemetics; in the event a dose of ruxolitinib is vomited, it is recommended that subjects resume ruxolitinib with the next scheduled dose.	

Event Name	Diarrhea
Grade of Event	Management/Next Dose for Ruxolitinib
≤ Grade 1	No change in dose
Grade 2	Hold until ≤ Grade 1. Resume at same dose level.
Grade 3	Hold* until < Grade 2. Resume at one dose level lower, if indicated. **
Grade 4	Off protocol therapy
*Patients requiring a delay of >4 weeks should go off protocol therapy. **Patients requiring > two dose reductions should go off protocol therapy.	
Recommended management: Loperamide antidiarrheal therapy Dosage schedule: 4 mg at first onset, followed by 2 mg with each loose motion until diarrhea-free for 12 hours (maximum dosage: 16 mg/24 hours) Adjunct anti-diarrheal therapy is permitted and should be recorded when used.	

Event Name	Thrombocytopenia
Platelet Count	Management/Next Dose for Ruxolitinib
50,000-100,000	Level 1 Ruxolitinib
35,000-49,999	Level -1 (reduction) if determined to be secondary to Ruxolitinib per the discretion of the investigator or PI.
20,000-34,999	Level -2 (reduction)

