Less than 20,000	Hold* until platelet count is at least 50,000 then resume at one dose level lower if determined to be secondary to Ruxolitinib per the discretion of the investigator or PI. Transfuse as needed for bleeds.
*Patients requiring a delay of >4 weeks should go off protocol therapy. **Patients requiring > two dose reductions should go off protocol therapy.	

Treatment will be discontinued for any patient that experiences a Grade 4 non-hematologic toxicity that is possibly related to ruxolitinib.

Dose adjustments for grades 1-3 non-hematologic toxicity that is possibly related to ruxolitinib will be at the discretion of the investigator or PI.

With the exception of thrombocytopenia (see table above), dose adjustments for grades 1-4 hematologic toxicity that is possibly related to ruxolitinib will be at the discretion of the investigator or PI.

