- Cases of tuberculosis have been reported. In addition, one case of progressive multifocal leukoencephalopathy has been reported in one patient with myelofibrosis.

The AE profile of the compound has been assessed in 198 healthy volunteers, subjects with various degrees of renal (n=32) or hepatic (n=24) impairment, and in patients with RA (n=59) receiving ruxolitinib:

- AEs were, in general, mild and resolved without interventions.

A thorough QT study was conducted in 50 healthy subjects. There was no indication of a QT/QTc prolonging effect of ruxolitinib in single doses up to a supra-therapeutic dose of 200 mg indicating that ruxolitinib has no effect on cardiac repolarization.

The following is a list of AEs (Section 8.1) and the reporting requirements associated with observed AEs (Sections 8.3 and 8.4).

The clinical course of each event will be followed until resolution, stabilization, or until it has been determined that the study treatment or participation is not the cause.

Serious adverse events that are still ongoing at the end of the study period will necessitate follow-up to determine the final outcome. Any serious adverse event that occurs within 30 days after the study period and is considered to be possibly related to the study treatment or study participation will be recorded and reported immediately.

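### The dosing rules give no starting dose for hepatic impairment, although Section 1.2.3 advises a cut of about 50% and Section 4.2 admits some patients with reported cirrhosis

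*Combined protocol and SAP*

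**What the plan says.** Background advice. Section 1.2.3 states: "In patients with mild, moderate or severe hepatic impairment, the recommended starting dose based on platelet count should be reduced by approximately 50" per cent, followed by titration on safety and efficacy. The same section gives similar advice for moderate and severe renal impairment (creatinine clearance below 50 mL/min). For strong CYP3A4 inhibitors it says that "the total daily dose should be reduced by approximately 50" per cent.

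Operative rules. Section 6.1.1 says "Patients will receive Ruxolitinib at 15 mg twice daily orally", with no hepatic qualifier. In the Section 7 dose table, the row that begins "Level 1 (starting dose" gives 15 mg twice daily for creatinine clearance of 60 or more and 10 mg twice daily for 15-59; there is no hepatic column. Section 6.2 covers strong CYP3A4 inhibitors: "the dose of ruxolitinib should be capped at 10 mg twice daily", worded for patients with platelets of at least 50,000. The event tables in Section 7 cover nausea, vomiting, diarrhea and thrombocytopenia. Beyond those tables, Section 7 says: "Dose adjustments for grades 1-3 non-hematologic toxicity that is possibly related to ruxolitinib will be at the discretion of the investigator or PI".

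Eligibility. Section 4.2 excludes active hepatitis B or C, known biopsy-confirmed cirrhosis, and "a reported history of liver cirrhosis with a model for end-stage liver disease (MELD) score >20". It sets no bilirubin or transaminase limit.

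**The concern.** The pharmacology section advises a lower start in any degree of hepatic impairment, the eligibility criteria admit some patients who have it, and the dosing sections do not say what those patients should receive. An investigator who follows Section 7 disregards 1.2.3; one who follows 1.2.3 departs from Section 7. Two similar patients could therefore start at different doses, and the one treated by the table would lose a safety margin that the protocol itself describes.

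The omission looks unintended. The neighbouring advice on renal impairment and CYP3A4 inhibitors was turned into rules, and no reason is given for leaving the liver out. Section 1.3 justifies 15 mg twice daily by the cause of the cytopenias and does not discuss liver function as a factor in dose.

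**Working it through.** **1. Is there a hepatic starting rule anywhere?** The three related pieces of advice in 1.2.3, set beside the dosing rules:

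- Renal impairment: about 50% reduction advised at clearance below 50. Section 7 has a rule: 10 mg twice daily at clearance 15-59. Cut = 1 - 10/15 = 33%.
- Strong CYP3A4 inhibitor: about 50% reduction advised. Section 6.2 has a rule: cap of 10 mg twice daily, again a 33% cut, stated only for platelets of at least 50,000.
- Hepatic impairment (mild, moderate or severe): about 50% reduction advised. There is no rule in 6.1.1, 6.2 or 7.

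**2. Can such a patient enrol?** Yes. The MELD criterion excludes scores above 20, so reported cirrhosis without biopsy confirmation and with MELD of 20 or less is eligible. Non-cirrhotic impairment is eligible too, unless it comes with active hepatitis B or C or meets another exclusion.

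**3. What dose results by default?** Take clearance of 60 or more, no strong CYP3A4 inhibitor and no platelet-driven reduction. The start is 2 x 15 = 30 mg/day, which is the protocol's own dose.

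**4. How does it compare with a reduced start?**

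- 50% of the protocol's dose: 0.5 x 30 = 15 mg/day; 30/15 = 2.0.
- The protocol's own reduced level, 10 mg twice daily: 2 x 10 = 20 mg/day; 30/20 = 1.5. This is a 33% cut, which 1.2.3 does not state.

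**5. Does the direction depend on the base dose?** The 50% in 1.2.3 applies to a platelet-based dose, so no mg figure follows for this trial. Section 1.2.2 gives an approved range of 5 to 25 mg twice daily. Halved, that is 2.5 to 12.5 mg twice daily, and the ratio of 15 mg to these runs from 15/2.5 = 6.0 to 15/12.5 = 1.2. A halved dose would equal 15 mg twice daily only from a base of 15/0.5 = 30 mg twice daily, above the 25 mg maximum. Every base in the approved range therefore puts the default above the advised start, but the size varies too much to quote one ratio as the finding. The 6.0 end is not a fair reading either, because 1.3 sets a flat 15 mg twice daily despite low platelets.

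**6. Does another rule close the gap?** The CYP3A4 cap, the renal column and the platelet table lower the dose for some patients, but not because of liver function. The discretion in Section 7 applies to toxicity possibly related to ruxolitinib, so not to liver function at baseline.

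**The case against.** The best defence is that 1.2.3 is background and the authors adapted it freely. The renal rule uses a different clearance boundary and a smaller cut, and the CYP3A4 cap has a platelet condition. A departure from 1.2.3 is therefore not in itself a contradiction. That stands, but it explains a modified rule better than a missing one.

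There are also real mitigations. Active hepatitis B or C is excluded, which narrows the hepatic population. Chemistries are drawn within 48 hours before treatment and weekly in weeks 1-5, and blood counts at least every 72 hours over those weeks (Section 12.2). The half-life is about 3 hours without appreciable accumulation (1.2.3), although no hepatic half-life is given. Section 8 describes generally mild adverse events in a pool that includes "subjects with various degrees of renal (n=32) or hepatic (n=24) impairment", but gives no dose, duration or separate hepatic result. These points limit the consequence; they do not set a lower start.

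Underdosing is the strongest counterweight. Section 1.3 cites 67% mortality and a median of 35 days from diagnosis to death. It also lists hepatosplenomegaly and multi-organ failure among the manifestations, so abnormal liver tests may reflect the disease being treated. A bilirubin trigger could then reduce the dose in the sickest patients, and the documents supply no threshold. This objection holds, and it confines the required fix to reported cirrhosis.

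A reader might infer that the protocol overdoses these patients 1.5- to 2.0-fold. The documents do not support that: the 1.5 rests on a 33% cut that 1.2.3 never states, the 2.0 assumes that the 50% applies to this trial's flat dose, and neither is a measured exposure.

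**Conclusion.** The gap is real and modest. The protocol advises a reduced start in hepatic impairment, admits some patients who have it, and gives no rule for them, so by default they start at 30 mg/day. If the advice is applied to the protocol's own dose, the start would be 15 mg/day. That figure is an assumption about the base; the direction holds for every base within the approved range.

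It would go too far to conclude that patients will be harmed or that many of the 10 are affected. The documents give no hepatic exposure ratio, no prevalence of impairment and no hepatic safety result, so neither excess exposure nor the number affected can be estimated. Nor does the point affect the validity of the survival test. It is an inexpensive safety clarification that should be made.

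**What to change.** Add to the Section 7 starting-dose table that patients with reported cirrhosis admitted under 4.2 start at a reduced level. Either of two levels would do:

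- 10 mg in the morning plus 5 mg in the evening (15 mg/day, the 50% cut in 1.2.3, feasible with the 5 mg tablets described in 10.1.1); or
- at most 10 mg twice daily (20 mg/day), matching the column for clearance 15-59.

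State that the dose may be raised to 15 mg twice daily if tolerated; this has to be written down because Section 7 otherwise contains only reductions and holds. If clearance is also 15-59, use the lower of the two starting doses. Extending the rule to non-cirrhotic impairment, for instance by a bilirubin threshold, is an option for the clinical team and not part of the required change. If the sponsor prefers 15 mg twice daily for everyone, a sentence giving the reason would also remove the ambiguity.

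The cost is an amendment to one table, with no new data, and n = 10 and the 4-of-10 rule stay as they are. A few patients would start below the 15 mg twice daily named in the primary objective, with some risk of underdosing, which the permission to raise the dose limits. If the lower levels of the clearance 15-59 column are adopted as well, platelets of 20,000-34,999 would mean a hold, as that column already implies.
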